13.1. Institution and Investigator Selection	
14. FINANCING AND INSURANCE	23
15. PUBLICATION POLICY	23
16. REFERENCE LIST	24
Appendix 1a – Investigator Statement (SCTRU Copy) Appendix 1b – Investigator Statement (Investigator Copy)	
The Principles of ICH Good Clinical Practice	

GLOSSARY OF ABREVIATIONS

BAUS British Association of Urological Surgeons
CaCTUS Cancer Clinical Trials Unit, Scotland

CI Chief Investigator
CT Computed Tomography
CRF Case Report Form

EAU European Association of Urology ePLND Extended Pelvic Lymphadenectomy

GCP Good Clinical Practice
HE Haematoxylin and Eosin

ICH International Conference on Harmonisation
IDMC Independent Data Monitoring Committee
ISUP International Society of Urological Pathologists

LN Lymph Node

LNI Lymph Node Invasion
LNM Lymph Node Metastases
MRI Magnetic Resonance Imaging

NCCN National Comprehensive Cancer Network

NCITA National Cancer Imaging Translational Accelerator

NPV Negative Predictive Value

PET-CT Positron Emission Tomography – computed tomography

PHS Public Health Scotland

PSMA Prostate-specific membrane antigen
PSMA-PET PSMA Positron Emission Tomography

PSA Prostate-specific Antigen

RC Path UK Royal College of Pathologists

RCT Randomised Control Trial RP Radical Prostatectomy RT Radiation Therapy

SCTRU Scottish Clinical Trials Research Unit

SDV Source Data Verification

SUV max Max Standardised Uptake Values

TMG Trial Management Group

TNM Classification of Malignant Tumours

TSC Trial Steering Committee

TRIAL SUMMARY

Protocol ID In vivo PSMA Expression Analysis

Protocol Title Analysis of PSMA expression in prostate cancer and its relationship

with the presence of nodal metastases

Development Phase Feasibility Study

Aims 1. To determine the relationship of PSMA expression at the primary tumour and the risk of pelvic nodal metastases.

2. To develop relevant protocols and standardised procedures for future imaging studies in a surgical prostate cancer cohort.

3. To develop a platform to support multi-centre prospective study to evaluate PSMA expression in prostate cancer *in vivo*.

Primary Outcomes

1. To establish whether prostate tumours with high PSMA expression have enhanced risk of pelvic nodal metastasis.

2. To establish best practice and optimise protocols for multicentre application of PSMA PET/CT imaging.

Secondary Outcomes To evaluate the feasibility of a future large scale randomised controlled trial (RCT), and develop quality assurance measures across the study team/network

2. To develop a platform to carry out RCT to study the usefulness of novel imaging/biomarkers for evidence-based treatment decisions in patients at risk of pelvic nodal prostate cancer.

Study Design

To study 60 patients with high risk prostate cancer opting for surgical intervention. Eligible patients will be managed with radical prostatectomy (RP) and extended pelvic lymph node dissection (ePLND).

Patient Accrual

60 patients will be recruited over 6 months from 4 UK sites.

1. INTRODUCTION

1.1. Background

Surgery and radiation therapy are treatment options for patients with curable prostate cancer at the time of diagnosis. For those patients opting for surgery, radical prostatectomy (RP) and extended pelvic lymphadenectomy (ePLND) is recommended for tumours within the intermediate to high risk category, as judged by clinical parameters such as PSA levels, tumour Gleason score and TNM stage based on cross sectional imaging (e.g. CT or multi-parametric MRI) and isotope bone scans.

The decision to carry out a formal ePLND at the time of RP is widely debated. The guideline from the European Association of Urology recommends RP and ePLND to be performed when $a \ge 5\%$ risk of nodal disease is calculated based on a predictive tool such as the Briganti nomogram [1] (derived from a large cohort of surgical patients with histologic data). For those patients undergoing radiation therapy (RT), there is also significant uncertainty as to the consensus indication for extending the radiation field to include the entire pelvis, in addition to the prostatic bed. Again, there are developed predictive models like the Roach formula [2] to aid decision-making regarding nodal-coverage.

The current practice for both surgical and radiation intervention varies widely with regards to the coverage of the pelvic lymph nodes, dependent on clinician preference and local facilities/expertise. Hence, there is an urgent unmet need for additional tools to support patient stratification according to their respective risks of pelvic lymph node metastasis, in order to reduce the number/proportion of men undergoing ePLND that are later confirmed to have no histological evidence of nodal disease. Improved stratification of patients based on their need for ePLND dissection or not would reduce both costs and operating time in patients at "low-risk" of having metastatic nodal disease, as well as minimising unnecessary surgery related morbidities in terms of lymphocele formation, thromboembolic events, neurovascular and ureteric injury.

1.2. Pre-Clinical Data

Prostate-specific membrane antigen (PSMA) is a cell surface protein with significantly increased expression in prostate cancer cells when compared to other PSMA-expressing tissues such as kidney, proximal small intestine or salivary glands [3, 4]. Another advantage of PSMA as an imaging target is its transmembrane location with a large extracellular domain. Scintigraphy using ProstaScint® (antibody capromab pendetide) has been limited to the detection of non-viable tumor cells, as it targets the cytoplasmic PSMA domain. Other limitations of antibody-based tumor detection methods include their relatively long circulation time, leading to high background to signal ratios and subsequent reduced detection rates.

Methods have been developed to label PSMA ligands with ⁶⁸Ga, ⁹⁹mTc and ^{123/124/131}I, enabling their use for PET imaging, more scintigraphy options and radioligand therapy. The initial experience with PET/CT using (Glu-NH-CO-NH-Lys-(Ahx)-[68Ga (HBED-CC)] coupled to a binding motif to the extracellular domain of PSMA (referred to as 68Ga-HBED-PSMA thereafter) suggests its ability to detect recurrent prostate cancer as well as metastatic disease [5, 6, 7, 8]. The majority of reported literature with the use of PSMA based imaging utilised 68Ga-HBED-PSMA-11 as a highly specific tracer for PSMA. Increasingly 68Ga-HBED-PSMA-11 PET imaging is adopted in staging of patients with high risk primary and recurrent prostate

cancer. However, there is urgent need to obtain robust data from multi-centre prospective patients with intermediate to high risk prostate cancer. Importantly, none of the reported series on the use of PSMA PET incorporate formal benchmarking of a centralised PET reporting reference in their study design.

1.3. Clinical Data

To date, the use of ⁶⁸Ga-HBED-PSMA-11 has been reported to show widely varying data on sensitivity (33–85%) and specificity (82–100%) for the detection of prostate cancer recurrence and the detection of nodal metastases. A recent report of a retrospective single centre surgical cohort with intermediate to high risk prostate cancer undergoing surgical intervention suggested promising data on the use of PSMA PET/CT imaging [8]. All patients harbored a nomogram-calculated risk of lymph node metastasis (LNMs) >20%. 608 lymph nodes (LNs) containing 53 LNMs were detected during RP. LNMs were present in 12 of 30 patients (40%). ⁶⁸Ga-PSMA PET/CT scans identified 4 patients (33.3%) as LN true positive and 8 patients (66.7%) as false negative. Median size of ⁶⁸Ga-PSMA-PET/CT–detected versus undetected LNMs was 13.6 versus 4.3 mm (p < 0.05). Overall sensitivity, specificity, positive predictive value, and negative predictive value of ⁶⁸Ga-PSMA PET/CT for LNM detection were 33.3%, 100%, 100%, and 69.2%, respectively. Hence, LNM size appeared to impact on the diagnostic accuracy of ⁶⁸Ga-PSMA PET/CT to detect nodal disease. Similar findings were reported [9] with significantly larger LNs being positive on PSMA imaging than those negative on scan but harboring LNMs: 4.73 mm +/-1.45) and 2.73 mm +/- 1.29, respectively; P = 0.001).

These studies confirm the urgent need to further define the detection threshold of LNM size for detection by PSMA as well as additional biomarkers to improve the overall confidence of pelvic nodal staging in patients with high risk disease.

1.4. Trial Rationale

Despite no compelling survival benefit attributed to ePLND, the procedure is recommended by EAU Guidelines for patients' with a ≥5% risk of having lymph node invasion (LNI). ePLND is best considered a staging procedure, as subsequent treatment options may depend on the nodal status by histologic evaluation, i.e. whether the patient will be observed (no LNI), receive adjuvant whole pelvis RT (low volume LNI) or consider adjuvant androgen deprivation therapy (high volume metastasis).

Data from the British Association of Urological Surgeons (BAUS) Radical Prostatectomy audit demonstrates that only 39% of men with high-risk disease received a formal ePLND at the time of surgery[14]. This highlights the urgent need for accurate imaging modalities to allow identification of potential LNI and thus reduce the morbidity of over-treatment.

The proposed multi-centre functional imaging study is designed to test the value of ⁶⁸Ga-HBED-PSMA-11 radiopharmaceutical in PET/CT as a staging test to identify individuals with pelvic lymph node disease (as well as to identify those without lymph node involvement). If the use of ⁶⁸Ga-HBED-PSMA-11 shows promising results in this study, a randomised controlled trial can be developed in the future to formally study the impact of PSMA PET/CT in patient selection for treatment (surgery or radiotherapy). In addition, besides PSMA PET/CT, other functional imaging tracers/modalities can be incorporated into the optimised study pipeline as future multi-centre prospective studies.

The widely varied range of sensitivity and specificity observed with the use of ⁶⁸Ga-HBED-PSMA PET/CT imaging is likely multi-factorial, including highly variable patient selection criteria and no pre-defined standard imaging protocol. All published studies so far have tended to "lump" together heterogeneous patient populations or published with small number of patients with no or little attempt for patient stratification. We propose a standardised reporting method with central reviewing and oversight by the NCRI PET core lab at St Thomas' Hospital.

2. TRIAL OBJECTIVES

Aims:

- 1. To determine the relationship of PSMA expression at the primary tumour and the risk of pelvic nodal metastases.
- 2. To develop relevant protocols and standard of procedures for future imaging studies in a surgical prostate cancer cohort.
- 3. To develop a platform to support multi-centre prospective study to evaluate PSMA expression in prostate cancer *in vivo*.

Primary Outcomes:

- 1. To establish whether prostate tumours with high PSMA expression have enhanced risk of pelvic nodal metastasis.
- 2. To establish best practice and optimise protocols for multi-centre application of PSMA PET/CT imaging.

Secondary Outcomes:

- 1. To evaluate the feasibility of a future large scale randomised controlled trial (RCT), and develop quality assurance measures across the study team/network.
- 2. To develop a platform to carry out RCT to study the usefulness of novel imaging/ biomarkers for evidence-based treatment decisions in patients at risk of pelvic nodal prostate cancer.

3. TRIAL DESIGN

3.1. General Design

[figure not shown]
We propose to carry out a PSMA expression feasibility study in a cohort of patients with high risk prostate cancer (in the absence of clinical evidence for distant metastasis) opting for surgical intervention with radical prostatectomy (RP) and extended pelvic lymphadenectomy (ePLND). Sixty patients will be recruited from 4 centres within the United Kingdom, namely Addenbrookes Hospital, Cambridge; Queen Elizabeth University Hospital, Glasgow, University College London Hospital, London and St Bartholomew's Hospital, Barts Health NHS Trust, London. The study will include patients with NCCN (National Comprehensive Cancer Network) high-risk prostate cancer (as defined by one or more of the following: PSA \geq 20ug/L, Gleason sum score \geq 8, T-stage \geq cT3).

Patients with high risk prostate cancer being considered for radical prostatectomy and pelvic node dissection will have a PSMA PET/CT scan as part of standard of care imaging. Standard of care imaging will be as per local clinical practice (MRI/CT/bone scintigraphy/non-PSMA PET scans), with PSMA PET scan performed in lieu of isotopic bone scan.

Patients who have given signed or verbal informed consent and who have met all eligibility criteria will be enrolled into the trial.

Patients will be recruited from the participating centres within a 6 month period. These patients with high-risk disease will be managed as outlined in Figure 1.

Figure 1. Study outline

Template based extended pelvic lymph node dissection and approach for pathological evaluation of specimens

For patients recruited to this study, an ePLND will be performed at the time of RP, removing lymphatic tissue up to the bifurcation of the common iliac artery, along the external iliac (with the distal limit at the deep circumflex vein and femoral canal), the internal iliac vessels and the obturator fossa, as well as the fossa of Marcille. The lateral limit of the template is at the external iliac vein and the medial limit is the perivesical fat [1, 10]. All specimens will be submitted by the surgeon in separate formalin–filled containers, labelled according to their anatomical location, i.e. left/ right external iliac, left/ right internal iliac, left/ right obturator and left/right fossa of Marcille.

After dissection, specimens from all enrolled patients will be sent for histopathological examination in line with the International Society of Urological Pathology (ISUP) consensus conference [11] and the UK Royal College of Pathologists (RCPath) dataset [12] by designated uropathologists at the study sites. RP specimens will be processed according to routine clinical protocol of the study sites. Lymphatic tissue will be examined by palpation, visual inspection and sectioning at 3 mm intervals, in accordance with a consensus protocol within this study. The transversely sliced lymph nodes (LNs) will be processed, paraffin-embedded and histological sections cut and stained for Haematoxylin and Eosin (H&E). Disease positivity will be defined as the presence of any metastatic deposits of prostate cancer in the LNs examined. For each metastatic LN, both the short axis and largest diameter (expressed in mm) of the metastatic deposits will be recorded. The number of positive nodes and the total number of nodes found will be reported for each of the nodal specimens submitted.

PSMA PET imaging and reporting

Lesions detected by PSMA imaging will be evaluated by their maximum Standardised Uptake Values (SUVmax), which provides an objective quantification of each abnormal lesion, with particular interest for the pelvic lymph nodes, but signals in the prostate, bone and other soft tissue if present will also be assessed. There is a small chance of potential occult distant metastasis being identified in PSMA PET/CT imaging. Regardless of the results of the PSMA PET imaging, ePLND will include clinically recommended anatomical template. Following surgery, the need for additional investigation to clarify the validity of PSMA PET/CT revealed signals will be at the discretion of the clinical team and will not be dictated by the trial. For instance, increased uptake in solid organs or bone may result from Paget's disease or haemangioma, which may require additional correlative imaging.

Images from ⁶⁸Ga-PSMA PET/CT scanning will be interpreted by two experienced nuclear medicine physicians (one at the local scanning site as well as central reporting by an expert nominated from the PSMA imaging subgroup). All LNs with increased ⁶⁸Ga-PSMA accumulation will be assigned to their respective anatomical location, measured in the short axis, along with an assigned SUVmax for each affected LN. In addition, visual analysis of the ⁶⁸Ga-PSMA uptake will included a four-point certainty scoring scale (definitely negative, equivocal probably negative, equivocal probably positive, definitely positive). Although not our primary research focus, PSMA +ve lesions within the prostate will be categorised as either focal or diffuse. Disease involving only one of the four prostatic quadrants will be considered as focal. If prostatic lesions are detected in more than one quadrant, the disease will be classified as diffuse/multifocal (if non-contiguous). Signals that indicate potential distant metastatic sites will also be scored using the four-point certainty scoring scale as described above for pelvic nodes [13].

Attention will be paid to ensure comparable imaging protocols are used across participating sites to ensure data obtained are suitable for objective and robust reporting of PSMA PET/CT across the study. Lesion uptake will be categorised according to a predefined anatomical scoring template.

Image scoring

Interpretation of PET imaging will be performed in accordance with the NCRI PET framework. All positive LNs on ⁶⁸Ga-PSMA PET/CT will be assigned to the respective anatomical region: left/right external iliac; left/right internal iliac, left/right obturator; left/right fossa of Marcille. Positive matching will be defined as the correlation between PET scan positivity and histological positivity, with histopathological analysis of the LNs considered the reference standard. Positive nodes in each nodal region/chain will be scored individually. These data can then be analysed separately or collectively for each nodal region. Once recruiting sites have satisfied QC evaluation by the UK PET Core Lab, the SUV values will be generated by identical (or very similar) reconstruction algorithms and are expected to be reproducible across the study.

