3.5. Endpoints

Primary Outcomes:

- 1. To establish whether prostate tumours with high PSMA expression have enhanced risk of pelvic nodal metastasis.
- 2. To establish best practice and optimise protocols for multi-centre application of PSMA PET/CT imaging.

Secondary Outcomes:

- 1. To evaluate the feasibility of a future large scale randomised controlled trial (RCT), and develop quality assurance measures across the study team/network.
- 2. To develop a platform to carry out RCT to study the usefulness of novel imaging/biomarkers for evidence-based treatment decisions in patients at risk of pelvic nodal prostate cancer.

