9. STATISTICS

9.1. Sample Size

If we identify 60 eligible patients we will formally analyse the relationship between PSMA expression in primary tumour and the incidence of pelvic nodal disease.

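### Primary-tumour PSMA uptake is the predictor in primary outcome 1, yet the reading rules call it a side issue and record no value when no prostate lesion is called

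*Protocol*

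**What the plan says.** Three places in the protocol agree on the main question.

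- Section 2, aim 1: "To determine the relationship of PSMA expression at the primary tumour and the risk of pelvic nodal metastases".
- Section 3.5, primary outcome 1: "To establish whether prostate tumours with high PSMA expression have enhanced risk of pelvic nodal metastasis".
- Section 9.1: with 60 eligible patients, "we will formally analyse the relationship between PSMA expression in primary tumour and the incidence of pelvic nodal disease".

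Section 3.1 sets out how the scans are read. Under PSMA PET imaging and reporting it gives a general rule, "Lesions detected by PSMA imaging will be evaluated by their maximum Standardised Uptake Values (SUVmax), which provides an objective quantification of each abnormal lesion", and continues "with particular interest for the pelvic lymph nodes, but signals in the prostate, bone and other soft tissue if present will also be assessed". The more detailed reading rules that follow assign an SUVmax to each affected lymph node. On the prostate they say "Although not our primary research focus, PSMA +ve lesions within the prostate will be categorised as either focal or diffuse", and then define the two categories by quadrant.

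Section 9.3 trains a logistic regression on SUV values from the PET/CT to predict metastatic disease. It does not say whether these are prostate or nodal values. Section 8.1 lists the PSMA PET/CT report as the imaging item that reaches the trial database.

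**The concern.** The predictor of the first-listed primary outcome is described, in the section that tells readers what to record, as something the study is not mainly about. A reader who follows that section will concentrate on the nodes.

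The practical consequence lies in the general SUVmax rule. It attaches a value to a detected lesion and takes in the prostate only where there is a signal. A man with no called prostate lesion leaves the reading with no number for the primary. He is by definition at the low end of PSMA expression, and so belongs to the group against which high expression is to be compared. If such men drop out of the regression, they are lost because of their predictor value, and the range of the predictor is cut from below.

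**Working it through.** **Reading the sections against each other.**

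1. Sections 2, 3.5 and 9.1 all take the primary tumour as the place where PSMA expression is measured and nodal disease as the outcome.
2. Section 3.1 puts the emphasis elsewhere ("with particular interest for the pelvic lymph nodes") and states that prostate lesions are not the main focus. On its plain reading this conflicts with step 1.
3. Section 3.1 still quantifies the prostate: the SUVmax rule covers every detected lesion and the same sentence names the prostate. A man with a called prostate lesion therefore has at least one value.
4. For a man without a called lesion, the rule that "signals in the prostate, bone and other soft tissue if present will also be assessed" yields nothing to record. No other sentence asks for a background or whole-gland value.
5. Section 9.3 does not resolve this, because its SUV values could be prostatic, nodal or both.

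**Illustration of size.** The protocol gives 60 patients with no alpha, power, effect size or event rate, so there is no planned figure to reproduce.

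Inputs:
- n = 60 (section 9.1).
- Node-positive rate 12/30 = 40% (the cohort cited in section 1.3), so 0.40 × 60 = 24 expected node-positive men.
- Assumed: odds ratio of 2.0 or 2.5 per SD of prostate SUV; 5%, 10% or 20% of men with no called prostate lesion, taken as those with the lowest uptake.

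Model: logit P(node-positive) = a + ln(OR) × x, with x standard normal and a set so that the mean risk is 0.40. Power is the share of simulated trials with Wald |z| > 1.96. With 3,000 trials the simulation error near 66% is √(0.66 × 0.34 / 3000) ≈ 0.9 points.

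Men left if the lowest group is dropped: 60 × 0.95 = 57, 60 × 0.90 = 54, 60 × 0.80 = 48.

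| No recorded value | OR 2.0, dropped | OR 2.0, kept at floor | OR 2.5, dropped | OR 2.5, kept at floor |
|---|---|---|---|---|
| 0% | 66% | 66% | 87% | 87% |
| 5% | 58% | 66% | 78% | 86% |
| 10% | 51% | 65% | 73% | 86% |
| 20% | 40% | 64% | 58% | 84% |

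The floor is the lowest SUV among men with a detected lesion. At an odds ratio of 2.0 and 20% missing, dropping costs 66 − 40 = 26 points and the floor value costs 66 − 64 = 2 points. Handling therefore decides almost the whole loss.

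**The case against.** Four arguments run the other way.

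- **The clause can be read narrowly.** Grammatically it may qualify only the sorting into focal and diffuse, not the measurement of uptake. That reading is possible. The plainer one, that prostate lesions are not the focus, remains, and a reading rule for a primary predictor should not need interpretation.
- **The protocol nowhere says that men without a called lesion are excluded.** They are observably not high expressers and could be classed as low or set to a floor value. This stands, and it limits the size of the point. But a floor is a substitute for a measurement that could simply be taken.
- **The value could be measured later.** Section 5.2.1 has the Core Lab collate the scans and asks sites to keep raw data for reprocessing. This also stands. However, no such re-reading is planned, and one done after pathology is known would be open to bias.
- **A SAP, not shown here, could define the predictor.** It could choose prostate over node and one value per man. It could not supply a number that readers were never told to record.

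Two stronger readings are tempting. A reader might infer that prostate uptake is reduced to focal or diffuse. It is not, because the general SUVmax rule covers detected prostate lesions, and focal/diffuse is an added description. A reader might also infer that in multifocal disease the value depends on which lesion the reader picks. The protocol describes no such choice: each lesion is evaluated, and taking one of several recorded values is a derivation rule that a SAP can set.

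**Conclusion.** The point holds in a limited form. The reporting rules in section 3.1 conflict with aim 1, primary outcome 1 and section 9.1 on whether the primary tumour is the focus. As written, they also leave men with no called prostate lesion without a recorded predictor value.

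The harm is conditional. If those men are dropped, power at an assumed odds ratio of 2 falls from about 66% to 58%, 51% or 40% for 5%, 10% or 20% missing. If they are kept at a floor value, the loss is about 2 points or less (up to 3 at an odds ratio of 2.5). The odds ratios and missing fractions are assumptions, the 40% rate comes from one cited cohort, and the protocol claims no power for this feasibility study. If every primary has a called lesion, nothing is lost and only the conflict in wording remains. The change is worth making because it is cheap and gives the first primary outcome a value for every man, not because the trial fails without it.

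**What to change.** 1. In section 3.1, PSMA PET imaging and reporting, delete the opening clause that says prostate lesions are not the primary research focus. Keep focal/diffuse as a description.
2. In the same place, require the central reader to record a prostate SUVmax, the highest in the gland, for every man, whether or not a lesion is called.
3. In section 9.3, state that this patient-level prostate value is the predictor for primary outcome 1, and keep it separate from nodal SUV.

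Maxima for the left and right halves of the gland are optional.

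The cost is one extra field on the PET form and a few minutes per scan for a central reader already in the design, on images the Core Lab already collates. No extra scan, patient or reader is needed, and patient care does not change.
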